6.3.1 Central Review of PET/CT

All patients will have a retrospective central review PET/CT (PET#1, PET#2, PET#3, and PET#4) for research purposes. As scans are performed in real time, a de-identified image of the PET should be sent for reviewed at the Northwestern University by [name]

Results of central reads will not be reported in real time and will therefore not be the determinant for patient care. Findings will be communicated to participating sites retrospectively, including any discrepancies between the central research read and local radiology read.

PET/CT scans should be de-identified and put on CD disks as DICOM files to be shipped to Northwestern QAM (See address below). Disks should be shipped with a completed Imaging Shipping Form (See NOTIS for Imaging Shipping Form). At the time of shipping, QAM should be notified ([contact]), and can provide any specific shipping instructions. Scans will be stored electronically at Northwestern.

Shipping address:

Clinical Trials Office – Quality Assurance Robert H. Lurie Comprehensive Cancer Center Northwestern University [name]

6.1.1.1 Analysis Using Total Metabolic Volume

We will measure the total metabolic tumor volume, TMTV, to estimate the total tumor burden and correlate with outcome. We will utilize methodology recommended by the European Association of Nuclear Medicine for solid tumors and widely used for Hodgkin lymphoma. 41

6.4 Endpoint assessment

6.4.1 Primary Endpoint

Our primary endpoint is to assess rate of complete response following pembrolizumab alone on FDG-PET (PET#2). This will be performed following three cycles of pembrolizumab on week 10. The scheduling window is day 64 +/-3 days. Negative PET is defined as Deauville score of 1-3 as assessed by central review. Patients will be considered evaluable for this endpoint if they have received at least one dose of pembrolizumab.

6.4.2 Secondary Endpoints

Toxicity Endpoints

The frequency and severity of adverse events by type, severity (grade), timing, and attribution to pembrolizumab will be assessed once per cycle according the NCI-CTCAE version 4.03. All patients who receive at least one dose of pembrolizumab will be evaluable for toxicity endpoints.

Efficacy Endpoints

Response and progression will be evaluated using the LUGANO 2014 Response Criteria⁴⁶.

Patients treated with pembrolizumab consolidation will also have disease assessed by the updated immune response criteria⁴⁷ in addition to LUGANO response criteria as an exploratory assessment.

6.4.3 Relapsed Disease (RD)

RD includes the following:

 Lymph nodes should be considered abnormal if the long axis is more than 1.5 cm regardless of the short axis. If a lymph node has a long axis of 1.1 to 1.5 cm, it should only be considered abnormal if its short axis is

43

44

more than 1.0. Lymph nodes \leq 1.0 x \leq 1.0 cm will not be considered as abnormal for relapse or progressive disease;

- Appearance of any new lesion more than 1.5 cm in any axis during or at
 the end of therapy, even if other lesions are decreasing in size.
 Increased FDG uptake in a previously unaffected site should only be
 considered relapsed or progressive disease after confirmation with other
 modalities. In patients with no prior history of pulmonary lymphoma, new
 lung nodules identified by CT are mostly benign. Thus, a therapeutic
 decision should not be made solely on the basis of the PET without
 histologic confirmation;
- At least a 50% increase from nadir in the sum of the product of the diameter (SPD) of any previously involved nodes, or in a single involved node, or the size of other lesions (eg, splenic or hepatic nodules). To be considered progressive disease, a lymph node with a diameter of the short axis of less than 1.0 cm must increase by ≥ 50% and to a size of 1.5 x 1.5 cm or more than 1.5 cm in the long axis;
- At least a 50% increase in the longest diameter of any single previously identified node more than 1 cm in its short axis;
- Lymphoma confirmed by repeat biopsy.

6.4.4 Progression Free Survival (PFS)

PFS will be defined as the length of time from treatment on protocol until the first occurrence of disease relapse, progression, re-initiation of cytotoxic chemotherapy, or death due to disease, or until last contact if the patient did not experience any of these from the end of treatment through two years of follow up.

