4.2.2.2.2 For those with a positive PET #3 (Deauville 4.5)

PET- Adapted Treatment for patients <60 with positive

Patients age <60 with Deauville score of 4-5 on PET#3 may transition to escBEACOPP (escalated bleomycin, etoposide, doxorubicin, cyclophosphamide, vincristine) +/radiation therapy (RT) at the investigators' discretion

- a. Patients with stage I/II disease may transition to 2 cycles of escBEACOPP +/- RT
- b. Patients with stage III/IV disease may transition to 4 cycles of escBEACOPP +/- RT

24

Initial Version date: March 10th, 2017

Amendment 6: March 29th, 2019

c. Patients with progressive/relapsed disease as defined in section 6.1.2.1 will be taken off study.

Patients 60 or older with a Deauville score of 4, 5 positive PET #3 will continue on AVD for a total of four- six cycles of AVD, depending on stage and tolerability.

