4.4.2 Prohibited Concomitant Medications

Subjects are prohibited from receiving the following therapies during the trial:

- Antineoplastic systemic chemotherapy or biological therapy
- Immunotherapy not specified in this protocol
- Chemotherapy not specified in this protocol

- Investigational agents other than pembrolizumab
- Patients requiring radiation therapy (except as specified in the protocol for those age < 60 with a Deauville score of 4-5 on interim PET/CT (PET#3)) will be taken off study.
- Live vaccines within 30 days prior to the first dose of trial treatment and while participating in the trial. Examples of live vaccines include, but are not limited to, the following: measles, mumps, rubella, varicella/zoster, yellow fever, rabies, BCG, and typhoid vaccine.
- Systemic glucocorticoids during and within 1 week of treatment for any purpose other than to modulate symptoms from an event of clinical interest of suspected immunologic etiology.

NOTE: The use of physiologic doses of corticosteroids may be approved after consultation with the PI.

NOTE: Dexamethasone is permitted as a pre-medication only during AVD chemotherapy.

Subjects who, in the assessment by the investigator, require the use of any of the aforementioned treatments for clinical management should be removed from the trial. Subjects may receive other medications that the investigator deems to be medically necessary.

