4.6.3 Subject Withdrawal/Discontinuation Criteria from Treatment and/or Overall Study

Subjects may withdraw consent at any time for any reason or be dropped from the trial at the discretion of the investigator should any untoward effect occur. In addition, a subject may be withdrawn if enrollment into the trial is inappropriate, the trial plan is violated, or for administrative and/or other safety reasons. Specific details regarding discontinuation or withdrawal are provided in Table 4.1.

A subject must be discontinued from the trial for any of the following reasons:

- Patient voluntarily withdraws from treatment (follow-up permitted)
- The subject or legal representative (such as a parent or legal guardian) withdraws consent (no follow-up permitted).
- Confirmed radiographic disease progression
- Note: For unconfirmed radiographic disease progression, please see Section 5.1.6
- Unacceptable toxicity/adverse experiences as described in Section 4.4
- Intercurrent illness that prevents further administration of treatment
- Investigator's decision to withdraw the subject (i.e. continuation not in the patient's best interest)
- The subject has a confirmed positive serum pregnancy test
- Patient develops a second malignancy that requires treatment which would interfere with this study
- Noncompliance or inability to comply with trial treatment or procedure requirements
- The subject is lost to follow-up
- Administrative reasons

The End of Treatment and Follow-up visit procedures are listed in Section 5 (Protocol Flow Chart). After the end of treatment, each subject will be followed for 30 days for adverse event monitoring (serious adverse events will be collected for 90 days after the end of treatment as. Subjects who discontinue for reasons other than progressive disease will have post-treatment follow-up for disease status until disease progression, initiating a non-study cancer treatment, withdrawing consent or becoming lost to follow-up. After documented disease progression each subject will be followed by telephone for overall survival until death, withdrawal of consent, or the end of the study, whichever occurs first.

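### PFS counts new treatment as an event only if it is cytotoxic, so patients leaving for off-protocol radiotherapy or a non-cytotoxic drug are credited with event-free time that nobody assesses

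*Combined protocol and SAP*

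**What the plan says.** Section 6.4.4 measures PFS from treatment on protocol to "the first occurrence of disease relapse, progression, re-initiation of cytotoxic chemotherapy, or death due to disease". For all other patients the time runs "or until last contact if the patient did not experience any of these from the end of treatment through two years of follow up". The list contains one treatment-based event, and it is limited to cytotoxic chemotherapy.

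Three other rules decide what happens to a patient who needs some other treatment:

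- **Section 4.4.2.** "Patients requiring radiation therapy (except as specified in the protocol for those age < 60" and Deauville 4-5 on PET#3) come off study. The prohibited list also covers biological therapy and "Immunotherapy not specified in this protocol". Subjects who "require the use of any of the aforementioned treatments for clinical management should be removed from the trial".
- **Section 4.6.3.** Patients who stop for reasons other than progression "will have post-treatment follow-up for disease status until disease progression, initiating a non-study cancer treatment, withdrawing consent or becoming lost to follow-up".
- **Section 5.0, footnote 7.** Survival contact, by visit or telephone, continues every 12 weeks for 2 years from the last dose of study drug. Section 4.6.2 also plans clinic visits every 3 months for up to 2 years for patients off treatment for any reason.

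Section 10.3.2 plans Kaplan-Meier curves and a 3-year PFS. It attaches no target rate or test to them.

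**The concern.** Two patients with the same residual, non-progressing disease can receive opposite PFS outcomes. The one given cytotoxic salvage has an event. The one given radiotherapy or a non-cytotoxic drug does not, and is then carried forward as event-free to a contact that may come well after the last scan. Part of the endpoint is thus set by the clinician's choice of treatment type.

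The direction is predictable: patients whose disease was not controlled to the clinician's satisfaction are kept as successes, which raises PFS. It also touches the trial's own rationale. Sections 1.3.1 and 2.1 give a reduced need for radiotherapy as an aim, yet unplanned radiotherapy leaves PFS untouched.

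**Working it through.** The documents state no PFS figure, so there is nothing to reproduce. The check is a reading of the rules together, followed by a sense of scale.

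**Following one patient through the rules**

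1. After chemotherapy the scan is still Deauville 4 or 5, with uptake reduced from baseline and no new lesion. Appendix C calls this a partial metabolic response that, at end of treatment, means residual disease. It is not progression, so there is no event yet.
2. No biopsy is taken. Section 6.4.3 would count biopsy-confirmed lymphoma as relapsed disease, but Section 6.4.4 does not require a biopsy before new therapy.
3. The clinician gives off-protocol radiotherapy or a non-cytotoxic drug. Section 4.4.2 removes the patient. Neither treatment is on the Section 6.4.4 list, so there is still no event.
4. Section 4.6.3 ends disease-status follow-up at the start of that therapy, so a later relapse need not be captured.
5. Survival contacts continue (Section 5.0, footnote 7). Section 6.4.4 uses last contact, not last disease assessment, as the end of event-free time. The interval between the two counts as event-free although disease was not being assessed.
6. If step 3 had been cytotoxic salvage, the patient would have had an event at that point.

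**Scale**

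Assumed inputs, none of them from the documents except N:

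- N = 26, the evaluable number in Section 10.2
- 4 patients with conventional PFS events
- 2 further patients who exit as in step 3 and have no later event
- full follow-up: every patient without an event, including the 2 exits, is still in contact when the fourth event occurs

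With no censoring before the last event, the Kaplan-Meier estimate is (N - events)/N.

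| Rule | Events | PFS |
|---|---|---|
| Section 6.4.4 as written | 4 | (26 - 4)/26 = 22/26 = 84.6% |
| Start of any non-protocol therapy is an event | 4 + 2 = 6 | (26 - 6)/26 = 20/26 = 76.9% |

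The difference is 2/26 = 7.7 points. Each reclassified patient moves the estimate by 1/26 = 3.8 points, or by 1/30 = 3.3 points at the full accrual of 30.

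**The case against.** **Much of the problem is already covered.** Biopsy-confirmed lymphoma counts under Section 6.4.3. Radiotherapy after a positive PET#3 under age 60, and pembrolizumab consolidation after a positive PET#3 at age 60 or over, are both on protocol. A later death due to disease still counts. All of this stands, and it narrows the affected group to patients without biopsy proof or progression who receive off-protocol radiotherapy or a non-cytotoxic drug. A reader might infer that PFS in general depends on the salvage chosen rather than on disease control. The documents support that only for this group.

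**Removal from the trial might end contact.** If the 2 illustrative patients had no contact after leaving, and left before all 4 events, the estimate would be 20/24 = 83.3%, which is 6.4 points above 20/26. But Sections 4.6.2 and 5.0 both plan continued contact, so last contact is not tied to the start of new therapy. The bias is present either way.

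**Counting any new therapy is an event-free-survival convention.** Section 10.0 itself mentions EFS, and censoring at new therapy is a recognised alternative for PFS. That is fair as a general matter. This plan, however, already counts new cytotoxic therapy as failure, so extending the rule to all non-protocol therapy is the consistent choice. The alternative belongs in a sensitivity analysis.

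**escBEACOPP.** It is cytotoxic, and Section 6.4.4 neither defines re-initiation nor exempts protocol chemotherapy. A reader might therefore infer that protocol escBEACOPP is a PFS event and that PFS is biased between age groups, since older patients with the same scan continue AVD. The documents do not support that as a finding. Section 4.2.2.2.2 says "Patients age <60 with Deauville score of 4-5 on PET#3 may transition to escBEACOPP", under a heading that treats AVD and escBEACOPP as alternatives for cycles 3 to 6. A transition within planned chemotherapy is not naturally a re-initiation. Nor can the number of such patients be sized from the PET-negative rates in Section 1.1.3. Those come from early-stage, non-bulky cohorts treated with ABVD, and one of them defines negativity as Deauville 1-2, where this trial uses 1-3. What remains is an ambiguity worth one clarifying sentence.

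**Conclusion.** The concern holds for a defined group: patients with no documented progression, relapse or biopsy-confirmed lymphoma who leave for non-protocol radiotherapy or a non-cytotoxic drug. For them the written rule records no event and credits unassessed time as event-free, whereas cytotoxic salvage would be an event. The Kaplan-Meier curve and 3-year PFS are biased upward.

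The documents do not say how many such patients to expect. The size is therefore conditional: 3.3 to 3.8 points per patient for N between 30 and 26, if each would otherwise stay event-free and in contact past the last event. The two-exit illustration rests on assumed counts.

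This is a change the sponsor should make, but it does not threaten the trial's main conclusion. PFS is descriptive, and the primary endpoint (complete response at PET#2) and the sample size do not depend on it.

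**What to change.** In Section 6.4.4:

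1. Replace re-initiation of cytotoxic chemotherapy with the start of any non-protocol anti-lymphoma therapy, including radiotherapy and non-cytotoxic drugs. Date the event at the start of that therapy.
2. Censor patients without an event at the last disease assessment rather than at last contact.
3. Report one sensitivity analysis that censors at the last disease assessment before new therapy.
4. As a clarification only, state that protocol-directed AVD, escBEACOPP with or without radiotherapy after a positive PET#3, and pembrolizumab consolidation are not events.

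No treatment rule changes. Section 5.0 already collects post-study anticancer therapy status at discontinuation and at survival follow-up; the form needs to capture the type of therapy and its start date. Because the event is dated at the start of new therapy, the end of disease-status follow-up in Section 4.6.3 no longer affects PFS for these patients. The cost is protocol wording and a PFS estimate that may look slightly less favourable.

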Grade >2 with confirmed myocarditis	Off protocol therapy. Admit to CCU (consider transfer to nearest Cardiac Transplant Unit). Treat as above. Consider high dose methylprednisolone Add ATG or tacrolimus if no improvement. Off treatment.		

*Including CHF, LV systolic dysfunction, Myocarditis, CPK, and troponin **Patients with evidence of myositis without myocarditis may be treated according as "other event"

Note: The optimal treatment regimen for immune mediated myocarditis has not been established. Since this toxicity has caused patient deaths, an aggressive approach is recommended.

4.5.3 **Diet/Activity/Contraception/Other Considerations**

Subjects should maintain a normal diet unless modifications are required to manage an AE such as diarrhea, nausea or vomiting.

Pembrolizumab may have adverse effects on a fetus in utero. Furthermore, it is not known if pembrolizumab has transient adverse effects on the composition of sperm. For this trial, male subjects will be considered to be of non-reproductive potential if they have azoospermia (whether due to having had a vasectomy or due to an underlying medical condition). Female subjects will be considered of non-reproductive potential if they are either:

> (1) post-menopausal (defined as at least 12 months with no menses without

Initial Version date: March 10th, 2017 34

Amendment 6: March 29th, 2019

an alternative medical cause; in women < 45 years of age a high follicle stimulating hormone (FSH) level in the postmenopausal range may be used to confirm a post-menopausal state in women not using hormonal contraception or hormonal replacement therapy. In the absence of 12 months of amenorrhea, a single FSH measurement is insufficient.); OR

- (2) have had a hysterectomy and/or bilateral oophorectomy, bilateral salpingectomy or bilateral tubal ligation/occlusion, at least 6 weeks prior to screening; OR
- (3) has a congenital or acquired condition that prevents childbearing.

Female and male subjects of reproductive potential must agree to avoid becoming pregnant or impregnating a partner, respectively, while receiving study drug and for 120 days after the last dose of study drug by complying with one of the following:

- practice abstinence[†] from heterosexual activity;
 OR
- (2) use (or have their partner use) acceptable contraception during heterosexual activity.

Acceptable methods of contraception are[‡]:

- Single method (one of the following is acceptable):
 - intrauterine device (IUD)

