⁵ Elderly patients may receive consolidation for a total of up to 1 or 2 years pembrolizumab treatment. Elderly patients who do not achieve CR after additional AVD will have pembrolizumab consolidation for up to 32 additional doses. Elderly patients with Stage III/IV disease who achieve CR after <6 cycles AVD will receive pembrolizumab consolidation for up to 14 additional doses. See section 4.2.3 for details.

⁶ See study schema in 1.2

⁷ Patients will be followed (either by routine clinic visit or by phone call) for survival every 12 weeks (±7 days) for 2 years from the last dose of study drug. Patients should also be monitored for occurrence of an allogeneic stem cell transplant within 24 months from the last study treatment. If patient undergoes an allo-SCT in this timeframe, transplant parameters and adverse events must be reported as specified in section 4.6.3 (up to 18 months from the time of SCT).

⁸ Vital Signs include: Blood pressure, pulse, respiratory rate, and oxygen saturation

⁹ See Appendix A

¹⁰ See Appendix D

¹¹ Comprehensive chemistry panel and CBC with differential are required within 14 days of study registration. Chemistry panel will include glucose, calcium, albumin, ALT, AST, sodium, potassium, total bilirubin, alk phose, and creatinine. CBC with differential must include Absolute Neutrophil Count.

¹² At baseline and every 6 weeks while on therapy with pembrolizumab.

¹³Patients must have HIV Ab screen; and Hepatitis B Sag, Sab, and core; and Hepatitis C Ab testing within 6 weeks of registration.

Trial Period:	Screening Phase	Treatment Cycles ¹						Off Rx	Surveillance			
		Pemb	orolizun	nab		AVD ^{2,3}		AVD ^{3,4}	sment	Pembrolizumab ⁵	Discont	Survival Follow-Up
Treatment Cycle/Title:	Main Study Screening	1	2	3	PET #2	1-2	PET #3	3-66	emo Asses	4-35		
Scheduling Window (Days):	Within 28 days of registration	1 ± 3	22 ± 3	43 ± 3	[64 ± 3	[120 ± 3	Post-Che	2-4 weeks after last dose of chemotherapy ± 3	30 days after last dose (pembro or AVD, ±5 days)	Every 12 weeks

²⁰ Adverse events will be followed for the first 30 days after treatment discontinuation. SAE's will be recorded for 90 days after treatment discontinuation. For patients who undergo allogeneic stem cell transplant (SCT) within 24 months of last study treatment, transplant parameters and adverse events will be recorded according to section 4.6.3 (up to 18 months from the time of SCT).

²¹ Echo or MUGA to be repeated after 4 cycles of doxorubicin

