6.4.5 Overall Survival (OS)

OS will be defined as time from study enrollment until death, or until last contact if the patient did not die from the end of treatment through two years of follow up.

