10.3.2 Analytic Plan for Secondary Objectives

To assess safety and tolerability, all adverse events will be summarized in terms of type, grade, timing and attribution to treatment. All enrolled patients who receive at least one injection of study drug or undergo a study-related procedure will be included in the safety analysis. The highest toxicity grades per patient will be tabulated for AEs and laboratory measurements, and the number and percent of patients reporting AEs will be quantified. Listings will be required for all on-study deaths, SAEs and AEs that lead to withdrawal from study. Narratives for all SAEs and deaths on-study will be required. These summaries will be done by age cohort.

Continuous toxicity monitoring will occur using the method of Ivanova et al.⁵¹ While this method may be used to identify an unacceptable level of toxicity after each patient, only values for every 5 patients will be given here. The following table gives the number of unacceptable toxicities that need to be observed after 5, 10, 15, 20, 25, 30 patients to identify an adverse toxicity rate exceeding 20% with a false positive rate (after each patient) of 2% and a desired probability of early stopping of 5%. Unacceptable toxicity is defined as any toxicity requiring discontinuation of pembrolizumab, as defined in Table 4.1.

Number of patients observed: 5 10 15 20 25 30 Number of observed toxicities: 4 6 8 9 11 12

Response assessment: Anti-tumor activity will be assessed using the LUGANO 2014 Response Criteria (Appendix C). Patients who receive consolidation with pembrolizumab will also have disease assessed by the Immune Response Criteria (Appendix F) as an exploratory assessment. To assess progression free survival

(PFS) and overall survival (OS), Kaplan Meier curves for progression and survival will be calculated for each cohort. The 3-year PFS will be determined from this curve for all patients

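### PFS counts a death only if it is due to disease, so a progression-free patient who dies of another cause is censored and the reported PFS is too high

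*Combined protocol and SAP*

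**What the plan says.** Section 6.4.4 opens: "PFS will be defined as the length of time from treatment on protocol until the first occurrence of disease relapse, progression". The sentence goes on to the remaining events and the rule for everyone else: "re-initiation of cytotoxic chemotherapy, or death due to disease, or until last contact if the patient did not experience any of these".

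Section 6.4.5 puts no such limit on death: "OS will be defined as time from study enrollment until death, or until last contact if the patient did not die".

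Section 10.3.2 plans Kaplan-Meier curves for progression and survival in each cohort and adds "The 3-year PFS will be determined from this curve for all patients". Section 10.2 also plans PFS for the total population and by age cohort. Neither section redefines PFS or names a competing-risk method. Section 10.0 calls the efficacy endpoint EFS, which the plan never defines by its events.

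**The concern.** The usual meaning of PFS is time to progression or death from any cause. Under section 6.4.4 a progression-free patient who dies of something other than lymphoma contributes no event. The plan does not use the word censored, but nothing else can follow from running that patient's time to last contact. Kaplan-Meier then treats the patient as someone who could still progress later. The curve is neither PFS in the usual sense nor a valid estimate of the cumulative incidence of progression. Each death also has to be classified by cause before it can be counted, and the plan describes no adjudication of cause.

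The point has some force in this trial. It enrols patients aged 60 and over, who section 1.3.1 says tolerate standard chemotherapy poorly. The note on immune-mediated myocarditis in section 4.5.2 says "Since this toxicity has caused patient deaths". A death from treatment is an outcome that a regimen chosen partly for tolerability should show in its PFS.

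**Working it through.** **Is there any repair elsewhere?** Setting the sections side by side:

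- 6.4.4: death is an event only when due to disease; patients with no listed event run to last contact.
- 6.4.5: any death is an OS event.
- 10.0, 10.2 and 10.3.2: EFS, PFS and OS are named and Kaplan-Meier is specified, with no change to the event list.
- 4.6.3: survival follow-up continues after progression, with no change to the PFS definition.

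So one non-disease death is an event in OS and not in PFS.

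**How large is the effect?** The plan states no PFS rate, target or event count, so there is no figure of its own to reproduce. The sizes below are illustrations.

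Inputs: N = 30 (maximum enrolment) or 26 (evaluable target), both from the plan. The progression count p, the number of non-disease deaths d, and the cohort size of 10 are assumptions. All patients are assumed to be followed to the landmark, with no other censoring.

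Formulas:

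- All-cause PFS = 1 − (p + d)/N.
- PFS as written, deaths before all progressions = 1 − p/(N − d).
- PFS as written, deaths after all progressions = 1 − p/N.

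Worked case, N = 30, p = 6, d = 1: all-cause 1 − 7/30 = 76.7%; as written 1 − 6/29 = 79.3% to 1 − 6/30 = 80.0%.

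| N | p | d | PFS as written (%) | All-cause PFS (%) | Difference (points) |
|---|---|---|---|---|---|
| 30 | 0 | 1 | 100.0 | 96.7 | 3.3 |
| 30 | 3 | 1 | 89.7–90.0 | 86.7 | 3.0–3.3 |
| 30 | 6 | 1 | 79.3–80.0 | 76.7 | 2.6–3.3 |
| 30 | 15 | 1 | 48.3–50.0 | 46.7 | 1.6–3.3 |
| 30 | 3 | 2 | 89.3–90.0 | 83.3 | 6.0–6.7 |
| 30 | 3 | 3 | 88.9–90.0 | 80.0 | 8.9–10.0 |
| 26 | 3 | 1 | 88.0–88.5 | 84.6 | 3.4–3.8 |
| 10 | 2 | 1 | 77.8–80.0 | 70.0 | 7.8–10.0 |

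A simulation of the worked case with uniform event times (20,000 runs) gave differences of 2.64 to 3.33 points, mean 2.97.

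**Can PFS lie above OS?** It can, if the small gap between enrolment and first treatment is ignored. With no progressions, one non-disease death gives PFS 100% and OS 96.7% (N = 30). With 6 progressors, all alive, it takes more: 7 deaths if they come late (80.0% against 1 − 7/30 = 76.7%), or 9 if they come early (1 − 6/21 = 71.4% against 1 − 9/30 = 70.0%). If every death were a PFS event and both endpoints had the same start, this could not happen.

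**The case against.** The strongest reply is that little depends on PFS here. It carries no hypothesis, target, power or decision rule, and section 10.0 calls the survival results preliminary. Non-disease deaths would not be hidden either: OS counts them, and section 10.3.2 says "Listings will be required for all on-study deaths", with narratives. All of that stands. It limits the importance of the point but does not correct a number that readers will take to include all deaths.

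A second reply is that the illustration does not describe 3-year PFS. Without consolidation, 9 weeks of induction, 16 to 24 weeks of chemotherapy and 104 weeks of follow-up give 129 to 137 weeks, short of 156. This partly stands. Section 4.6.3 follows patients who stop without progression until they progress, so 3-year data are not ruled out, but full follow-up to 3 years cannot be assumed. The figures therefore belong to a landmark at which follow-up is complete. They are not an upper bound later on: a death when n patients remain at risk lowers the all-cause curve by S/n, where S is its height just before. That exceeds 1/N once other censoring has made n smaller than N × S.

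Third, there is little evidence that such deaths are likely. The myocarditis note is general and does not document a death on pembrolizumab. Section 1.2.1 reports no drug-related grade 4 or 5 events among 23 patients on nivolumab and no serious adverse events among 15 on pembrolizumab. Those groups are small and the plan gives no rate, so such deaths can be neither predicted nor excluded.

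Finally, the endpoint also counts new cytotoxic chemotherapy and disease deaths, so it is not pure time to progression. Cause-specific PFS is the closer name, and the bias is the same.

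**Conclusion.** The concern holds on the plain text. As written, PFS is never below all-cause PFS, and it is above it whenever a non-disease death comes before a PFS event. In the full trial population, with complete follow-up to the landmark, the overstatement is about 3 to 4 points for one such death if progressions are few, and down to 1.6 points if half of 30 patients progress and the death precedes them all. It grows roughly in proportion to the number of deaths and is larger in a small age cohort. The event counts and the cohort of 10 are assumptions.

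The primary CR analysis, the sample size and its power are unaffected. This is a definition that should be corrected before the data are analysed, not a flaw in the main question of the trial.

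**What to change.** In section 6.4.4, make death from any cause a PFS event. If the narrower endpoint is also of interest, report it separately as time to progression, treat deaths from other causes as competing events, and present cumulative incidence. In section 10.0, either replace EFS with PFS or define it.

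The cost is one phrase and no new data. Section 5.0, footnote 7 already has patients followed "for survival every 12 weeks (±7 days) for 2 years from the last dose of study drug", and on-study deaths are already listed. Treatment, visits and sample size do not change. The only downside is that reported PFS may be slightly less favourable.
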